5.2 Adverse Events of Interest

- Autoimmune disorders, such as:
 - systemic lupus erythematosus
 - rheumatoid arthritis
- Demyelinating disorders, such as:
 - multiple sclerosis
 - Guillain-Barre syndrome
 - chronic inflammatory demyelinating polyneuropathy
- Serious infections including opportunistic infections, such as:
 - tuberculosis
 - pneumonia
- Lymphoma and other malignancies, such as:

- hepatosplenic T-cell lymphoma
- non-Hodgkin's lymphoma
- solid malignancies
- Acute hypersensitivity reactions occurring within 2 hours of drug administration, such as:
 - urticaria, rash, pruritus, flushing, swollen lips/tongue/pharynx, wheezing, dyspnea, hypotonia, cramping, abdominal pain, and vomiting
- Other events:
 - congestive heart failure
 - aplastic anemia, pancytopenia, thrombocytopenia, neutropenia and leucopenia
 - serious bleeding events
 - serious skin reactions (eg, Stevens Johnson Syndrome, toxic epidermal necrosis, and erythema multiforme)

When available, narrow scope SMQs (Standardized MedDRA Queries) from the Medical Dictionary for Regulatory Activities (MedDRA®) version 17.0 will be used to define the AEs of interest (Section 5.2). Adverse events of interest that are the clinical endpoints for the SECURE registry will be confirmed by review of the results of diagnostic tests and diagnostic criteria used by the Investigator which are further explained within each section below.

Table 5–1: Standardized MedDRA Queries for select adverse events of interest

Event	SMQ Title	SMQ Code	SMQ Scope
Malignancy	Malignant tumours	20000194	Narrow PTs
Congestive Heart Failure	Cardiac failure	20000004	Narrow PTs
Serious skin reactions	Severe cutaneous adverse reactions	20000020	Selected Narrow PTs
Hypersensitivity reactions	Anaphylactic reaction	20000021	Narrow/Broad PTs
Serious bleeding events	Haemorrhage	20000038	Narrow PTs
Aplastic anemia	Haematopoietic cytopenias affecting more than one type of blood cell	20000028	Narrow PTs
Aplastic anemia	Haematopoietic erythropenia	20000029	Narrow PTs

Table 5–1: Standardized MedDRA Queries for select adverse events of interest

Event	SMQ Title	SMQ Code	SMQ Scope
Aplastic anemia	Haematopoietic leukopenia	20000030	Narrow PTs
Aplastic anemia	Haematopoietic thrombocytopenia	20000031	Narrow PTs

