For events in which SMQs are not available, MedDRA v 17.0 Preferred Terms (PT) for the System Organ Class (SOC) and High-Level Group Term (HLGT) categories will be used as appropriate. For AEs of interest, where no SMQ is available, medical review will occur to select AEs (eg demyelinating disorders, autoimmune disorders and serious infections). Additional detail on the clinical validation of the primary endpoints is presented below although all safety events that meet the definition of AEs of interest will be collected and summarized as part of the study.

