5.2.9 Serious skin reactions

For this category, primary endpoints are Erythema multiforme, Stevens Johnson's syndrome, and Toxic epidermal necrolysis.

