8.2.3 Adverse Events of Interest

The AEs of interest and the approach for summarizing them is briefly described below. Further information is provided in the guidance document (AEs of Interest – Cimzia Program 2018-01-05).

- Serious infections, including opportunistic infections. Serious infections will be summarized using the Serious TEAE table. In addition, opportunistic infections (including tuberculosis) will be presented in a table using UCB-defined search criteria.
- Malignancies, including lymphoma. These will be presented in 2 tables using the Standardized MedDRA Query (SMQ) criteria “Malignant or unspecified tumours” and “Malignant tumours” respectively.
- Serious cardiovascular events (also called major adverse cardiac events or MACE). These will be presented in a table including all serious TEAEs with the SMQs of “Haemorrhagic central nervous system vascular conditions”, “Conditions associated with central nervous system haemorrhages and cerebrovascular accidents”, and “Ischaemic central nervous system vascular conditions” with the exception of events coding to a PT of “Transient ischaemic attack”, including all serious TEAEs with the HLT of “Ischaemic coronary artery disorders” except events coding to PTs of “Chest Pain” or “Chest discomfort” and including all serious TEAEs with HLTs of “Heart Failures NEC”, “Left Ventricular Failures”, or “Right Ventricular Failures” and which also code to the SOC of “Cardiac Disorders”.
- Congestive heart failure. These will be manually identified by the study physician from the TEAE table.
- Demyelinating-like disorders will be presented in table which is based on the SMQ = “Demyelination”. The SMQ search should include all TEAEs which code to a PT included in Scope=Narrow group within the SMQ. TEAEs which code to a PT included in the Scope=Broad group within the SMQ should be excluded from the search.
- Aplastic anemia, pancytopenia, thrombocytopenia, neutropenia, and leucopenia. These will be presented in a table using the criteria SMQ = “Haematopoietic cytopenias” in the subset of Serious TEAEs.
- Serious bleeding events. These will be presented in a table using the criteria SMQ = “Haemorrhage terms (excl laboratory terms)” in the subset of Serious TEAEs.
- Lupus and lupus-like illness. These will be manually identified by the study physician from the TEAE table.

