- Serious skin reactions (eg, Stevens-Johnson Syndrome, toxic epidermal necrosis, and erythema multiforme). These will be manually identified by the study physician from Serious TEAE table.

Although not officially AEs of interest, the following events will also be summarized as described in the AEs of Interest – Cimzia Program 2018-01-05 guidance document.

- Hepatic events. These will consist of a subset of all TEAEs, identified using the following 5 SMQs: Cholestasis and jaundice of hepatic origin; Hepatic failure, fibrosis, and cirrhosis and other liver damage-related conditions; Hepatitis, noninfectious; Liver-related investigations, signs and symptoms; and Liver-related coagulation and bleeding disturbances.
- Hypersensitivity reactions and anaphylactic reactions. Hypersensitivity reactions will be summarized as any TEAEs occurring on the same day or the day after injection was received, which code to the following preferred terms: Administration site hypersensitivity, Documented hypersensitivity to administered product, Drug hypersensitivity, Hypersensitivity, Hypersensitivity vasculitis, Infusion site hypersensitivity, Injection site hypersensitivity, Medical device site, hypersensitivity, Type II hypersensitivity or Type IV hypersensitivity reaction. Anaphylactic reactions will be defined using an algorithmic approach as described in the “AEs of Interest – Cimzia Program 2018-01-05” guidance document.
- Specific to study and not from the “AEs of Interest – Cimzia Program 2018-01-05” guidance document, we will also look at Malignant Lymphomas using the Narrow PTs from the “Malignant Lymphomas” SMQ, and into Autoimmune disorders and Lupus/Lupus-Like syndromes.
- Specific to study and not from the “AEs of Interest – Cimzia Program 2018-01-05” guidance document, we will also look at cases of non-melanoma Skin Cancer. These will be manually identified by the study physician from the TEAE table.

Table 8.1: Overview of malignancy events and acute events in this study

Overview of Events	
Event	Event Type (Malignancies are in addition analyzed following acute rules)
Malignant or unspecified tumor	Malignancy
Malignant tumor	Malignancy
Non melanoma skin cancer	Malignancy
Malignant Lymphoma	Malignancy
Serious infection	Acute
Opportunistic infection	Acute
Serious cardiac event	Acute
Congestive heart failure	Acute
Demyelinating-like disorder	Acute
Aplastic Anemia	Acute
Serious bleeding	Acute
Lupus and Lupus-like illness	Acute

Serious skin reaction	Acute

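### SAP 8.2.3 has the study physician pick out congestive heart failure and serious skin reactions by hand, where Protocol Table 5-1 assigns each a coded MedDRA query, and it states no masking to treatment

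*SAP*

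**What the plan says.** SAP 8.2.3 sets out how each adverse event of interest is found. Under CHF it reads: "Congestive heart failure. These will be manually identified by the study physician from the TEAE table". For serious skin reactions it gives three diagnoses as examples and then: "These will be manually identified by the study physician from Serious TEAE table". Neither entry names a Standardized MedDRA Query (SMQ), a list of preferred terms, a diagnostic criterion or a second reader.

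Protocol 5.2 sets a different rule. The events of interest are defined as follows: "When available, narrow scope SMQs (Standardized MedDRA Queries) from the Medical Dictionary for Regulatory Activities". Table 5-1 gives CHF the Cardiac failure SMQ (20000004), narrow terms. It gives serious skin reactions the SMQ titled "Severe cutaneous adverse reactions" (20000020), with scope "Selected Narrow PTs". Selection by review is provided for elsewhere: "For AEs of interest, where no SMQ is available, medical review will occur to select AEs", with demyelinating disorders, autoimmune disorders and serious infections as the examples. Protocol 6.1.1 adds that the SAP will supply the specific codes.

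The protocol also has a clinical layer. Endpoint events are confirmed against diagnostic tests and criteria (5.2), CHF is defined by the Framingham criteria (5.2.6), and for skin the "primary endpoints are Erythema multiforme, Stevens Johnson's syndrome, and Toxic epidermal necrolysis" (5.2.9).

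**The concern.** Both events are compared between Cimzia and comparator. SAP 2.2.1 lists them for incidence rates, event rates and time-to-event statistics, 8.1.3 produces hazard ratios, and 8.1.4 produces rates and a Poisson regression. The case definition therefore feeds directly into a comparison.

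Under SAP 3.6, adverse event tables use actual treatment unless otherwise specified, and the physician is told to select from those tables. Nothing in either document hides treatment at this step. The SAP in force is dated 1 September 2020 (12.5), after the study end of 28 August 2020 (2.3), so the accumulated data are available when the cases are chosen. If the choice leans even slightly on known treatment, the rate ratio moves for reasons unrelated to the drug. A coded search applied identically to both groups removes that discretion, and the protocol had already specified one.

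**Working it through.** **Step 1. Set the rules side by side.**

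| | Protocol | SAP 8.2.3 |
|---|---|---|
| CHF, case finding | SMQ 20000004, narrow terms (Table 5-1) | Manual, study physician, from the TEAE table |
| CHF, confirmation | Diagnostic review, Framingham criteria (5.2, 5.2.6) | Not mentioned |
| Skin, case finding | SMQ 20000020, selected narrow terms (Table 5-1) | Manual, study physician, from the serious TEAE table |
| Skin, named diagnoses | Three (5.2.9) | The same three, as examples |
| Selection by medical review | Where no SMQ is available (5.2) | Used although Table 5-1 has an SMQ |

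All of this is current text in both documents. SAP section 1 says the plan was developed from protocol amendment 5, and the amendment rationales in SAP section 12 do not explain the change.

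**Step 2. Is a coded search workable here?** Yes. SAP 8.2.3 itself uses coded searches for malignancy, serious cardiovascular events, demyelination, cytopenias, bleeding and hepatic events. The serious cardiovascular category already captures serious heart failure through three high-level terms, so one report would count heart failure by two methods.

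**Step 3. How far does the contradiction extend?** It is complete for CHF. For skin it is partial: Table 5-1 fixes the SMQ but not which narrow terms are selected, so a choice of terms was always left open, bounded by the three diagnoses in 5.2.9. Lupus and non-melanoma skin cancer are also identified by hand in SAP 8.2.3, but neither has a line of its own in Table 5-1.

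**Step 4. What could it do to a ratio?** The documents give no event rate or count for either endpoint, so there is no plan figure to reproduce. For illustration, assume no false positives:

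observed ratio = true ratio × (selection sensitivity under Cimzia ÷ selection sensitivity under comparator)

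With a true ratio of 1.0 and assumed sensitivities:
- 0.90 and 0.95: 0.90 ÷ 0.95 = 0.95
- 0.80 and 0.95: 0.80 ÷ 0.95 = 0.84
- 0.95 and 0.80: 0.95 ÷ 0.80 = 1.19
- equal sensitivities, as a treatment-independent search aims for: 1.0

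These sensitivities are not in the documents. The illustration shows direction and order of size only.

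**The case against.** **The mechanism is not described.** Selecting from a table may mean choosing preferred-term rows, and each row applies to both treatment columns. Treatment could then influence which terms are chosen, but not which patients count within a term. This stands as an ambiguity: the SAP does not say whether terms or patients are selected. A reader might infer that the counts are biased, and the documents do not show that.

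**The detail may be elsewhere.** SAP 8.2.3 describes its approach as brief and points to a separate guidance document on events of interest, which is not among the documents reviewed and may hold search terms. That limits what can be said about missing criteria, but SAP 8.2.3 still prescribes manual identification. The SAP also cites that guidance under two dates (2018-06-18 in 2.2.1, 2018-01-05 in 8 and 8.2.3), so the reference alone does not settle the definition.

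**The count can be checked.** A reader might infer that it cannot be reproduced at all. That is too strong: SAP 8.2.2 tabulates events by preferred term and lists those collected on the case report form, so an SMQ count can largely be rebuilt. What cannot be rebuilt from the documents is the physician's own selection.

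**The protocol wants clinical review.** It does, as confirmation. A definition by SMQ alone would drop that layer, so it is not the right repair.

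**The effect is small.** Malignancy, the primary outcome, uses SMQs. Neither event has a power target in Protocol 6.3, and all analyses are descriptive. With an assumed 10 cases per group and equal time, the approximate 95% interval for a ratio of 1.0 is exp(±1.96 × √(1/10 + 1/10)), or 0.42 to 2.40. Moving 2 cases in one group gives 12/10 = 1.2 or 8/10 = 0.8, well inside that interval. This limits the weight of the point. It does not remove it, because the interval reflects chance and not systematic selection.

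**Conclusion.** The SAP departs from the protocol for two comparative acute endpoints, fully for CHF and in part for serious skin reactions. Case selection could depend on known treatment because tables are by actual treatment by default and SAP 8.2.3 states no masking or criteria. The size is unknown: the documents give no counts, and every figure above rests on assumed inputs.

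Two further inferences should be resisted. The SAP says study physician and does not give an employer, so it does not support saying that a sponsor employee chooses the cases. Nor does the contradiction extend to lupus or non-melanoma skin cancer, which lack their own SMQ in Table 5-1.

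The point should be corrected because the repair is cheap and restores a rule already specified. It does not threaten the primary outcome.

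**What to change.** In SAP 8.2.3:

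1. Make the Table 5-1 SMQs the case-finding rule for both events: 20000004 with narrow terms for CHF, and 20000020 with the selected terms written out for skin, covering at least the three diagnoses in Protocol 5.2.9. If the guidance document holds a term list, cite it by one date and reconcile it with Table 5-1.
2. Keep physician review as the protocol's confirmation step, with the Framingham criteria for CHF. Do it from a listing without treatment or cohort columns, and log each decision before exposure is merged.
3. Report the SMQ-based and the confirmed counts side by side.
4. For lupus and non-melanoma skin cancer, keep manual identification but use the same kind of listing.

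The cost is SAP wording, a term list and one extra listing, with no new data collection. There are two downsides. Counts may differ from earlier interim reports. Masking may also be imperfect: under SAP 8.2.2 the study physician has already reconciled investigator reports with the drug safety database, and under Protocol 5.6 the sponsor's safety database takes registry events within 70 days of the last Cimzia dose, so an event's presence there can hint at exposure. A reader who took no part in the reconciliation would mask better, at some cost in staff time.

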5.2.7 Aplastic anemia

Aplastic anemia is a primary endpoint. Diagnosis must be confirmed by complete blood count (CBC) with peripheral smear, and bone marrow biopsy. Findings of pancytopenia (neutropenia, thrombocytopenia, and anemia), a reduction in the absolute number of reticulocytes, and a hypocellular bone marrow could be used to confirm the diagnosis.

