2.2 Study variable(s)

2.2.1 Primary variable(s)

The primary outcome of this observational study is malignancy (malignant tumors and malignant or unspecified tumors). Additionally, the following safety events will be presented using incidence and event rates, and time-to-event statistics:

- Serious infections
- Opportunistic infections
- Serious cardiovascular events (also called major adverse cardiac events, or MACE)
- Congestive heart failure
- Demyelinating-like disorders
- Aplastic anemia, pancytopenia, thrombocytopenia, neutropenia and leucopenia
- Serious bleeding events
- Lupus and lupus-like illness
- Serious skin reactions

Although not officially AEs of interest, the following events will also be summarized as described in the AEs of Interest – Cimzia Program 2018-06-18 guidance document.

- Hepatic Events
- Hypersensitivity reactions and anaphylactic reactions

Separate from the AEs of interest document, malignant lymphomas, non-melanoma skin cancer, and autoimmune disorders will also be summarized.

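### The event that SAP Table 8.1 labels aplastic anemia is any serious cytopenia, and no rate or hazard ratio is planned for aplastic anemia confirmed as Protocol 5.2.7 requires

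*SAP*

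**What the plan says.** Protocol 5.2.7 states: "Aplastic anemia is a primary endpoint. Diagnosis must be confirmed by complete blood count (CBC) with peripheral smear, and bone marrow biopsy". Protocol 6.1.1 names malignancy as the primary outcome and lists aplastic anemia, by itself, among the other safety events to be investigated. It points back to Protocol 5.2 for the coding and clinical validation.

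Protocol 5.2 lists aplastic anemia together with pancytopenia, thrombocytopenia, neutropenia and leucopenia as one item of interest. Protocol Table 5-1 assigns four queries to the event aplastic anemia, all limited to narrow terms: multi-lineage cytopenias, erythropenia, "Haematopoietic leukopenia" and thrombocytopenia. The same section says that adverse events serving as clinical endpoints will be confirmed against diagnostic tests and criteria.

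SAP 2.2.1 carries the five-part item as "Aplastic anemia, pancytopenia, thrombocytopenia, neutropenia and leucopenia". SAP 8.2.3 defines it: "Aplastic anemia, pancytopenia, thrombocytopenia, neutropenia, and leucopenia. These will be presented in a table using the criteria", followed by the Haematopoietic cytopenias SMQ, "in the subset of Serious TEAEs". It mentions neither narrow scope nor confirmation. Table 8.1 lists the event as "Aplastic Anemia", to be analysed under the acute-event rules. There is no second row.

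**The concern.** The protocol describes two stages: a broad search for cytopenias, then confirmation of the endpoint. The SAP text keeps only the search and, in Table 8.1, gives its result the name of the confirmed endpoint. Applied literally, a patient hospitalised with an isolated low platelet count, or with a neutropenia that resolves, is counted in the row named aplastic anemia.

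Protocol 3 names aplastic anemia among the serious risks of the TNF-blocker class. If outputs use the Table 8.1 name, a Cimzia-versus-comparator hazard ratio for mixed serious cytopenias could be read as evidence about aplastic anemia. An effect confined to aplastic anemia would be diluted in that ratio by any commoner single-lineage cytopenias.

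**Working it through.** **1. No figure to reproduce.** The sample-size text (Protocol 6.3, SAP 2.4) covers serious infections, lymphoma and solid malignancies. Neither document gives a rate, count or effect size for aplastic anemia or cytopenia, so the check compares definitions.

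**2. Definitions side by side.**

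| Element | Protocol | SAP |
|---|---|---|
| Search | Four cytopenia queries (Table 5-1) | Haematopoietic cytopenias SMQ (8.2.3) |
| Term scope | Narrow | Not stated |
| Seriousness | No limit in Table 5-1 | Serious events only |
| Confirmation | "Diagnosis must be confirmed by complete blood count (CBC) with peripheral smear, and bone marrow biopsy" (5.2.7) | Not stated |
| Name | Aplastic anemia (6.1.1, Table 5-1); five-part item (5.2) | Five-part item (2.2.1, 8, 8.2.3); aplastic anemia (Table 8.1) |

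The SAP is more specific for neighbouring events in 8.2.3: an explicit narrow-scope rule for demyelination, and identification by the study physician for heart failure, lupus-like illness and serious skin reactions. The amendment rationales in SAP 12 mention updated SMQs but no decision to drop confirmation.

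**3. What will be estimated.** Time-to-event analyses (SAP 8.1.3) and incidence and event rates (SAP 8.1.4) are run per adverse event of interest. With one row in Table 8.1, these apply to the composite. SAP 8.2.2 and 8.2.4 add counts and percentages by preferred term, serious-event tables and a listing, all unconfirmed and without person-years. SAP 8.1 allows analyses of specific outcomes but commits to none.

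**4. Direction.** Protocol 5.1 gives aplastic anemia/pancytopenia as an example of an event to report as serious, so the serious filter should lose few or no true cases. If every confirmed case is coded within the SMQ and recorded as serious, confirmed cases are a subset of the composite.
- Event rate: same person-time and at least as many events, so the composite rate is equal or higher in every treatment group.
- Incidence rate, all groups together: at least as many patients with an event and no more person-time, so again equal or higher. Within one group, the only exception is a patient whose first serious cytopenia occurred under a different treatment, because SAP 8.1.4 treats the later event as a recurrence.

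**5. Size, for illustration only.** Let *s* be the share of composite events that are confirmed aplastic anemia (in the comparator group, for the ratio) and *R* the true rate ratio for aplastic anemia, with no effect on other cytopenias. Then composite rate ÷ confirmed rate = 1/*s*, and composite rate ratio = 1 + *s*(*R* − 1). With *R* = 3:

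| Assumed *s* | 1/*s* | Composite ratio |
|---|---|---|
| 50% | 2 | 1 + 0.50 × 2 = 2.00 |
| 25% | 4 | 1 + 0.25 × 2 = 1.50 |
| 10% | 10 | 1 + 0.10 × 2 = 1.20 |
| 5% | 20 | 1 + 0.05 × 2 = 1.10 |
| 2% | 50 | 1 + 0.02 × 2 = 1.04 |

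Both *s* and *R* are assumptions.

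**6. What a separate row could show.** With an assumed 1 to 10 confirmed cases per 100,000 patient-years, the planned 25,000 patient-years (Protocol 6.3) give 25,000 × 0.00001 = 0.25 to 25,000 × 0.0001 = 2.5 expected cases. With zero cases, the exact Poisson upper 95% limit is −ln(0.025) = 3.689 events. That is 3.689 ÷ 12,500 × 100 = 0.0295 per 100 patient-years at the planned person-time per arm. For 1371 Cimzia patients, 8 years and 8% annual drop-out, person-time is 1371 × (1 − 0.92⁸) ÷ (−ln 0.92) ≈ 8,004 patient-years, and the limit is 3.689 ÷ 8,004 × 100 = 0.0461. Time at risk under the acute rules stops after last dose plus the exposure window, so the real limits may be wider.

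**The case against.** The strongest reply is that the protocol is itself broad. Its list of events of interest has the same five conditions, Table 5-1 already maps single-lineage queries to aplastic anemia, and 5.2 plans to collect and summarise all events of interest. This stands as far as it goes: a reader might infer that the SAP introduced the broad coding, and it did not. The SAP's serious-only limit is even narrower than Table 5-1. But 5.2 separates that summary from validation of the endpoints, and 5.2.7 makes confirmation mandatory.

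A reader might also take "Aplastic anemia is a primary endpoint" to mean the study's main outcome. That fails: Protocol 6.1.1 and SAP 2.2.1 give that place to malignancy, and Protocol 5.2 names primary events or endpoints for every category.

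The claim that aplastic anemia is never reported would go too far as well. A preferred-term count by treatment group and a serious-event listing are planned, so a coded case would be visible. Missing is a committed rate or hazard ratio for confirmed cases.

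The label problem is confined to Table 8.1, an overview that shortens other names too; SAP 2.2.1, 8 and 8.2.3 give the composite in full, and no output shells are available. Finally, the SAP is to be read with the protocol, and 8.2.3 is a brief description that defers to a guidance document not available here. It therefore cannot be said that the study performs no confirmation, only that the SAP states none.

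**Conclusion.** The point holds in limited form. Following the SAP as written gives an incidence rate and a hazard ratio for mixed serious cytopenias, and neither for aplastic anemia confirmed under Protocol 5.2.7. If the Table 8.1 name reaches the outputs, the figure read as an aplastic anemia rate can only equal or exceed the confirmed one, subject to the coding and seriousness assumptions and the first-event exception in the working.

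The size is unknown. A reader might infer from the illustration that most labelled events are not aplastic anemia; the documents contain no cytopenia rates and do not support any particular share. All analyses are descriptive (SAP 2.1.1) and confirmed cases are likely to be very few, so no formal test is distorted. What changes is whether the final report can describe a named class risk under the protocol's own definition. The correction should be made because it is specific and cheap.

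**What to change.** - In SAP 8.2.3 and Table 8.1, rename the composite as serious haematopoietic cytopenias and state whether narrow or broad SMQ terms are used.
- Add a separate row for aplastic anemia confirmed as Protocol 5.2.7 requires, with number of patients, incidence rate and exact Poisson 95% interval by the method already in SAP 8.1.4. Give a hazard ratio only if the number of events allows it. State how a reported case with no biopsy result on file is shown.
- Relabel the single-lineage rows of Protocol Table 5-1 (erythropenia, leukopenia, thrombocytopenia) to match. If the protocol will not be amended again, record the mapping in the SAP.
- If the sponsor prefers the composite alone, document and justify the departure from Protocol 5.2.7 and do not use the aplastic anemia label for it.

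The cost is SAP wording and one table row. The diagnostic review is already required by Protocol 5.2, so no new data collection is proposed. The row will probably be little more than a case count with an interval.

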5 ADVERSE EVENTS OF INTEREST, SERIOUS ADVERSE EVENTS, CASE AND EXPOSURE DEFINITIONS

Serious adverse events and AEs of interest are the focus of this registry; Investigators are not expected to enter nonserious AEs in the eCRF except for AEs of interest regardless of seriousness.

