5.2.8 Serious bleeding events

For this category, bleeding events meeting the criteria of an SAE are primary endpoints.

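### SAP 8.2.3 counts cytopenias as events of interest only when serious, although the protocol defines and collects them without a seriousness limit

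*SAP*

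**What the plan says.** **Protocol.** Section 5.2 names "aplastic anemia, pancytopenia, thrombocytopenia, neutropenia and leucopenia" as events of interest. The bleeding and skin-reaction bullets that follow carry the word serious; this one does not. Table 5-1 assigns four haematopoietic queries to the group, narrow scope, the first being "Haematopoietic cytopenias affecting more than one type of blood cell", with no seriousness filter. On collection, section 5 says that "Investigators are not expected to enter nonserious AEs in the eCRF except for AEs of interest regardless of seriousness". Section 5.2 adds that "all safety events that meet the definition of AEs of interest will be collected and summarized as part of the study". Section 5.2.7 states "Aplastic anemia is a primary endpoint", again with no seriousness condition.

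**SAP.** Sections 2.2.1 and 8 list the same five terms, without the word serious, among the events to receive incidence and time-to-event summaries. Section 8 refers to 8.2.3 for what each event means. Section 8.2.3 then takes the haematopoietic cytopenias query "in the subset of Serious TEAEs". It gives no reason for the restriction, states no query scope for this group, and plans no event-of-interest analysis of cytopenias of any seriousness. Table 8.1 labels the row simply as aplastic anemia.

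**The concern.** The SAP's case rule is narrower than the protocol's event. Where the protocol wants a seriousness restriction, it writes one: in section 5.2.8, "bleeding events meeting the criteria of an SAE are primary endpoints". It does not do so for cytopenias, and it asks sites to enter the nonserious ones.

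Three things are at stake. The event-of-interest rates would describe a different event from the one the protocol defines. The comparison would rest on fewer events than were collected, so it would be less precise. And the output would be open to misreading: a row called aplastic anemia, next to rows explicitly called serious infection, serious bleeding and serious skin reaction, invites the reader to take a serious-only rate for an all-event rate.

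**Working it through.** The documents give no rate, sample size or power for cytopenias, so there is no planned figure to reproduce. The check is a comparison of text, followed by an illustration under stated assumptions.

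**Step 1. Trace the definition to the results.** SAP 2.2.1 promises incidence rates, event rates and time-to-event statistics for the group. SAP 8 links those summaries to 8.2.3. SAP 8.1.3 (hazard ratios) and 8.1.4 (rates) take their events from that definition. The serious filter therefore decides which cases enter the numerators and the Cox models. It does not govern the general tabulations in 8.2.2, which cover all adverse events by coded term, or the listing of all events entered on the eCRF.

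**Step 2. Identify which cases are affected.** Protocol 5.1 gives aplastic anemia and pancytopenia as examples of important medical events to be reported as serious. Those cases should mostly pass the filter. The loss falls mainly on nonserious leucopenia, neutropenia and thrombocytopenia.

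**Step 3. Effect on precision.** Let d1 and d0 be the event counts in the two groups, and let s be the share that is serious, equal in both.

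- All events: SE(log RR) = sqrt(1/d1 + 1/d0).
- Serious only: SE = sqrt(1/(s·d1) + 1/(s·d0)) = SE(all) / sqrt(s).
- The reported rate becomes s times the rate of collected events.

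For scale, assume 80 collected first events, split equally, with equal person-time. Then SE = sqrt(4/(80s)). The rate ratio detectable with 80% power at two-sided 0.05 is exp((1.960 + 0.842)/sqrt(80s × 0.25)). Neither the 80 nor the range of s comes from the documents.

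| s | events kept | SE inflation | SE | detectable RR | power at RR 2.0 |
|---|---|---|---|---|---|
| 1.0 | 80 | 1.00 | 0.224 | 1.87 | 87% |
| 0.8 | 64 | 1.12 | 0.250 | 2.01 | 79% |
| 0.5 | 40 | 1.41 | 0.316 | 2.43 | 59% |
| 0.2 | 16 | 2.24 | 0.500 | 4.06 | 28% |

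The SE inflation depends only on s. The last three columns also depend on the assumed 80 events. The SAP calls its analyses descriptive, so the power column only translates the loss of precision into familiar terms.

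**Step 4. Effect on the ratio.** If the serious share is sC on Cimzia and sK on comparator, the serious-only ratio equals the all-cytopenia ratio × sC/sK. Take an all-cytopenia ratio of 1.5:

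- Equal shares (0.3 and 0.3): 1.5 × 0.3/0.3 = 1.5, unchanged.
- Shares 0.2 and 0.4: 1.5 × 0.2/0.4 = 0.75.
- Shares 0.4 and 0.2: 1.5 × 0.4/0.2 = 3.0.

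These shares are also assumed. They show that the shift can go either way or not occur.

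**The case against.** The case for leaving the SAP alone has several parts.

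- **The named endpoint is largely intact.** Protocol 6.1.1 lists only aplastic anemia among the further events to be investigated, and aplastic anemia should mostly be reported as serious. This stands, and it narrows the point to the milder cytopenias. It does not remove the point: protocol 5.2 and Table 5-1 define the wider group, and SAP 2.2.1 and 8 adopt it.
- **Nothing disappears from the report.** Nonserious cases stay in the general tables and listings, and SAP 8.2.2 treats an event as serious if either data source does. A reader might infer that the cases are discarded altogether; the documents do not support that. The loss is confined to the event-of-interest analyses.
- **Serious events are more uniformly ascertained.** The amendment history in protocol section 14 shows the five-term group joining the list of events of interest with Amendment 2 (December 2011), whereas the study began in January 2009. Nonserious cases were apparently not always requested in between. Protocol 4.4 and 4.5 add no monitoring and no mandatory visits, so detection of mild cytopenia depends on each site's routine blood testing. This is the strongest argument for the filter, and it is why an all-event row needs a caveat. But the SAP does not offer it, and it supports showing both rows rather than only one.
- **A guidance document holds the detailed definitions.** It is not available here. Nothing in the SAP suggests that it lifts the restriction.

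Two stronger readings are tempting. One is that the comparative safety signal is understated. Step 4 shows that this does not follow: the absolute rate is lower by definition, but the ratio may be unchanged or move in either direction. The other is that most cases are lost. No serious share in the documents supports that.

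**Conclusion.** The mismatch is real and lies in the current text of both documents. The SAP restricts the cytopenia event-of-interest analysis to serious events without a reason, against the protocol's definition and collection rule and against the SAP's own lists in 2.2.1 and 8.

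Its size cannot be computed from the documents. Under an assumed serious share of 0.8 to 0.2, equal in both groups, the standard error of the log rate ratio grows by a factor of 1.12 to 2.24. A serious-only ratio is a legitimate estimate for serious cytopenias. It misleads only if it is read as the protocol's event, and then the direction of the error is unknown. The conclusion on text needs no assumption, apart from the unseen guidance document not reversing the filter.

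**What to change.** In SAP 8.2.3, apply the cytopenia search to all study-emergent adverse events for the rates and time-to-event analysis. Use the protocol's narrow-scope haematopoietic queries and state the scope. Dropping the word serious is not enough by itself to restore the protocol's event: the SAP names one query with no scope where Table 5-1 names four narrow ones, and the dictionary version is 20.0 in SAP 3.7 against 17.0 in the protocol. The SAP should say how the two correspond.

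Report the serious subset as a second row labelled serious cytopenias, and relabel the row in Table 8.1 to match. Add a note that nonserious ascertainment varied across protocol versions and depends on routine monitoring, so the two rows should be read together.

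The cost is one extra row or table, a little programming and a change of SAP wording, using data already collected. The small downside is the less uniform all-event row, which the second row and the note address.
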